1. INTRODUCTION

This statistical analysis plan (SAP) document outlines the statistical methods to be implemented during the analysis and reporting of Study Protocol RVT-1201-2002, the double-blind phase, referred to as the Main Study. The purpose of this plan is to provide specific guidelines from which the analyses will proceed. Any deviations from these guidelines will be documented in the clinical study report (CSR). Analyses of the open-label extension (OLE) phase of the study will be described in a separate SAP and will be reported in a separate CSR.

This SAP supersedes the statistical considerations identified in the protocol; where considerations are substantially different, they are identified in [Section 11](#). Any post-hoc or unplanned analyses, or significant changes from the planned analysis in this SAP performed to provide results for inclusion in the clinical study report (CSR) but not included in this SAP, will be clearly identified in the CSR. Changes to planned analyses do not require an updated SAP but should be included in the CSR if significant.

2. INFORMATION FROM THE STUDY PROTOCOL

2.1. Study Objectives and Endpoints

[Table 1](#) describes the objectives and their corresponding endpoints. Note the endpoints are specified in order of the protocol specified *objectives*, and not the order of the *endpoints* specified in the protocol.

Table 1: Objectives and Corresponding Endpoints

Objectives	Endpoints/Criteria for Evaluation
Primary	

To evaluate the effect of rodatristat ethyl on the percent change from baseline of pulmonary vascular resistance (PVR), as measured by right heart catheterization (RHC) in patients with PAH	
Percent change from baseline to 24 weeks of PVR between an active arm and the placebo arm
Secondary	
To evaluate the effect of rodatristat ethyl from baseline to Week 24 on the following: 
WHO FC6MWDN-terminal pro-Brain Natriuretic (NT-proBNP)	To evaluate the effect of rodatristat ethyl from baseline to Week 24 on the following: 
Change from baseline in WHO FCChange from baseline in 6MWDChange from baseline in NT-proBNP
Safety	

To assess safety & tolerability of rodatristat ethyl in patients with PAH	
Change in safety parameters including AEs, vital signs, laboratory values, and electrocardiogram (ECG) assessments
Additional	

Hemodynamics (cardiac index, mean pulmonary artery pressure [mPAP], mean right atrial pressure	
Change from baseline in cardiac index, mPAP, mRAP, SvO₂ at rest and PAC

Objectives	Endpoints/Criteria for Evaluation

[mRAP], mixed venous oxygen saturation [SvO₂], and pulmonary artery compliance [PAC])
 
 Time to Clinical Worsening (TTCW) defined as the first occurrence of a composite end point of: 1. Death from any cause, 2. Hospitalization for worsening PAH (any hospitalization for worsening PAH, lung or heart and lung transplantation, atrial septostomy, or initiation of parenteral prostanoid therapy), 3. Disease progression defined as a decrease of more than 15% from baseline in the 6-minute walk distance (6MWD) combined with WHO FC III or IV symptoms at 2 consecutive visits separated by at least 14 days (adjudicated). Death from any cause Echocardiographic measures of right atrial size & RV function (tricuspid annular plane systolic excursion [TAPSE], tricuspid annular systolic velocity, and RV fractional area change) Pulmonary Arterial Hypertension-Symptoms and Impact Questionnaire (PAH-SYMPACT) Register to Evaluate Early and Long-Term PAH Disease Management (REVEAL) Lite 2 score 	
 TTCW All-cause mortality Change from baseline in right atrial size & RV function (TAPSE, tricuspid annular systolic velocity, & RV fractional area change) Change from baseline in PAH-SYMPACT Change from baseline in REVEAL Lite 2.0 Score

Exploratory
 
 Time to Clinical Improvement (TTCI) Actigraphy 	
 A > 10% increase in 6MWD or 30 meters AND an improvement to or maintenance of WHO FC II symptomatology, in the absence of a deterioration in clinical condition or death during the 24 weeks of the Main Study Change from baseline in actual daily activity, (counts/minute) as determined by actigraphy: 
 Light to vigorous activity/day Moderate to vigorous activity/day Total movement/day Best 6-minute walk effort

PK/PD (To be covered under a separate SAP)
 
 To assess the PK of rodatristat ethyl and metabolites To assess the effect of rodatristat ethyl on plasma and urinary 5-HIAA To evaluate the effect of rodatristat ethyl on the plasma concentration of selexipag and ACT 33367 	
 Population PK parameters of rodatristat ethyl, active metabolite rodatristat ethyl, M15, and other metabolites Change from baseline in 5-hydroxyindoleacetic acid (5-HIAA; plasma and spot urine concentration) Plasma selexipag and ACT 333679 trough concentration at baseline and Week 4

2.2. Double-Blind Phase Study Design

This study will compare the efficacy, safety, and tolerability of 2 dosing regimens of rodatristat ethyl to placebo in subjects with PAH over a 24 week treatment period. Investigational product (IP) will be administered on the background of stable PAH therapy.

Approximately ninety (90) evaluable subjects will be enrolled. Subjects will be randomized 1:1:1 to placebo, 300 mg BID, or 600 mg BID of rodatristat ethyl.

Eligible subjects will be stratified based on the number of background PAH therapies they are receiving (1 vs 2 vs 3) and selexipag use (Yes/No). The number of subjects who are on a prostanoid infusion will be capped at 50% of the total enrolled. The number of subjects who are receiving selexipag will be capped at 20% of the total enrolled.

The study will consist of a Screening Period (up to 28 days in duration), a Baseline Period (Day 1), a 24-week Treatment Period (Main Study), and for subjects that early terminate or do not enroll an Open Label Extension (OLE), and a 4 week Follow Up Period (approximately 4 weeks after the last dose), for a total study duration of 32 weeks.

Subjects who complete the Main Study will have the option to enroll into an OLE and continue to receive rodatristat ethyl (those randomized to placebo will be re-randomized 1:1 to receive rodatristat ethyl 300 mg BID or 600 mg BID) for 6.5 years, until the Investigator or subject chooses to stop the IP, any stopping criteria in the Main Study are met, IP becomes commercially available, or the Sponsor stops the study for lack of efficacy or a safety signal (whichever preceding criteria comes first). In no case will a subject be allowed to exceed 10 years of exposure unless the product is approved for a chronic indication.

All participating subjects will be required to be on a stable background therapy for PAH with mono, dual or triple combination therapy (which may include currently approved prostanoid therapies) at the time of Screening. All subjects will maintain their standard of care (SOC) regimen at entry for the duration of the study. Refer to Section 6.6.2 for more details.

During the 24 week Treatment Period, in addition to the Day 1/Baseline Visit and a telemedicine or phone call at Week 2, subjects will return to the study center for safety, tolerability and efficacy-related assessments at Weeks 4, 8, 12, and 24, and a clinic or home visit at Week 18, as specified in the Schedule of Events Table, Section 1.3, as well as Follow-up at Week 28 (as applicable). Female subjects of childbearing potential will undergo pregnancy testing every 4 weeks and will be required to use 2 reliable methods of contraception to reduce the risk of pregnancy, at Screening, during the course of the study, and for at least 4 weeks following the last dose of rodatristat ethyl. Additional pregnancy testing in women whose menstruation is delayed or who have infrequent or irregular menstrual cycles should be completed as warranted.

2.2.1. Study Procedures

The overall schedule of activities for the Main Study is outlined in Section 1.3 of the study protocol. See study protocol for complete details.

2.2.2. Study Drug

Study drug is defined as any investigational intervention(s), marketed product(s), or placebo intended to be administered to a study subject according to the study protocol. The IPs to be administered as part of this study are described in [Table 2](#).

Table 2: Study Drug

Treatment Name	300 mg BID*	600 mg BID*	Placebo*
Dose Formulation	Tablet	Tablet	Tablet
Unit Dose Strength(s)	300 mg	300 mg	N/A
Dosage Level(s)	1 x 300 mg tablet + 1 x placebo tablet BID	2 x 300 mg tablets BID	2 x placebo tablets BID
Route of Administration	Oral	Oral	Oral
IP	Rodatristat ethyl	Rodatristat ethyl	Placebo
Packaging and Labeling	IP will be provided in bottles. Each bottle will be labeled as required per country requirement.		

*The components in rodatristat ethyl are provided in Section 3.2.2, Table 1 of the Investigator's Brochure. The active and placebo are formulated with the same excipients.

Abbreviations: BID = twice daily; IP = investigational product; N/A = not applicable

IP will be taken BID with food, approximately 12 hours apart.

Each subject will receive at least 4 bottles (1 kit) of IP at each clinic visit or by mail. There is enough IP in each kit for 4 weeks of dosing, including overage. The bottles of IP given at each clinic visit or by mail should be returned at the subsequent clinic visit for reconciliation and accountability.

The last dose of IP for the Main part of the study will be the last dose the night before the Week 24 visit (all Week 24 assessments will be collected post last dose).

2.2.3. Treatment Assignment, Blinding, and Randomization Methodology

This is a double blind study, with an open label extension (covered under a separate SAP). The Sponsor, Investigator, subject, and study site personnel will be blinded to all treatment group assignments. The Investigator will have the ability, in the IRT system, to unblind a subject, and the decision will reside solely with the Investigator. Prior to unblinding, if safety allows, the Investigator should contact the Medical Monitor to discuss the reasons for unblinding.

Eligible subjects will be stratified during the randomization process based on the number of background PAH therapies they are receiving (1, 2 or 3) and selexipag use. The number of subjects who are receiving a prostanoid infusion will be capped at 50% of the total number of subjects enrolled. The number of subjects who are receiving selexipag will be capped at 20% of the total number of subjects enrolled. Subjects will be randomized 1:1:1 to placebo, 300 mg BID, or 600 mg BID of rodatristat ethyl using an interactive randomization system.

At the time of Screening for entry into the OLE, all subjects will be re-randomized to receive either 300 mg BID or 600 mg BID rodatristat ethyl in an open-label fashion. Subjects will not know what they received in the Main Study until all subjects have completed the Main Study and the database is locked.

At the time of randomization, in the Main Study, subjects will be assigned a randomization number. Once this number has been assigned, it cannot be reused/reassigned.

Emergency unblinding procedures are outlined in section 6.4 of the study protocol and in the unblinding plan.

3. SAMPLE SIZE JUSTIFICATION

The sample size for this study was not based on a formal hypothesis testing. It is expected that 30 evaluable subjects per arm will provide sufficient data to assess safety and efficacy. Power calculations were conducted to examine the probability of detecting a difference among treatment groups for the percentage change of PVR from baseline.

A sample size of 90 subjects with 30 subjects to be randomized into 1 of the 3 treatment arms in a 1:1:1 randomization is planned. A sample size of 30 subjects per arm will provide at least 80% power at a significance level of 0.05 (2-sided hypothesis) to detect a treatment difference of 0.75 times of standard deviation (SD) in the percentage change from baseline of PVR from baseline between an active arm and the placebo arm. If the SD for PVR percent change is 24%, the study has 80% power to detect a difference of 18% between an active arm and the placebo arm.

4. GENERAL STATISTICAL METHODS

4.1. Reporting Conventions

Individual subject data obtained from electronic case report forms (eCRFs), central laboratories, external sources, and any derived data will be presented in data listings by subject. The primary data source will be used for all analyses. All data listings that contain an evaluation date will contain a relative study day. Pre-treatment and on-treatment study days are numbered relative to the day of the first dose of study drug which is designated as Day 1. The preceding day is Day -1, the day before that is Day -2, etc.

All outputs will be incorporated into Microsoft Word rich text format (.rtf) files, sorted and labeled according to the International Council for Harmonisation (ICH) E3 guideline, E3 Structure and Content of Clinical Study Reports, and formatted to the appropriate page size(s), font type, and font size according to Food and Drug Administration (FDA) guidance of Portable Document Format Specifications.

For categorical variables, summary tabulations of the number and percentage of subjects within each category of the parameter will be presented. Percentage calculations will be based on non-missing data, unless otherwise specified. If there are missing values, the number missing will be presented, but without a percentage. Percentages are rounded to 1 decimal place, unless otherwise specified.

For frequency counts of categorical variables, categories whose counts are zero will be displayed for the sake of completeness. For example, if none of the subjects discontinue due to "Lost to Follow-up," this reason will be included in the table with a count of 0. Percentages will be presented to 1 decimal place, with the exception of 0, which will be presented without percent, and 100, which will be presented without decimal places. Values less than 0.1% will be presented as "<0.1%." Values less than 100% but greater than 99.9% will be presented as ">99.9%."

For continuous variables, the number of subjects, mean, standard deviation (SD), median, 25th (Q1) and 75th (Q3) percentiles, minimum, and maximum values will be presented. The precision of summary statistics, unless otherwise specified will be as follows: mean, median, Q1, and Q3 to 1 more decimal place than the raw data, SD to 2 decimal places more than the raw data, and minimum and maximum to the same decimal places as the raw data. In general, the number of decimal places should not exceed 3 decimal places unless appropriate.

Confidence intervals (CIs) will be provided and will be rounded to 1 decimal place, unless otherwise specified, in the table and listing shell. A full set of summary statistics will only be presented if 3 or more values are available. If there are less than 3 values, only the min, max, and N will be presented. The other summary statistics will be denoted as not calculated (NC).

For tables where rounding is required, rounding will be done to the nearest round-off unit. For example, when rounding to the nearest integer, values \geq XX.5 will be rounded up to XX+1 (e.g., 97.5 will round up to 98), while values $<$ XX.5 will be rounded down to XX (e.g., 97.4 will round down to 97).

All statistical tests comparing groups will be conducted at the 2-sided, 0.05 level of significance, unless otherwise specified. Summary statistics for each treatment group will be presented, as well as two-sided 95% CIs comparing groups will be provided.

4.2. Computing Environments

All descriptive statistical analyses will be performed using SAS software Version 9.3, unless otherwise noted.

Medical history and AEs will be coded using Medical Dictionary for Regulatory Activities (MedDRA) version 24.0. Concomitant medications will be coded using World Health Organization Drug Dictionary (WHODD), B3 Enhanced March 2021.

Study Data Tabulation Model (SDTM) and Analysis Data Model (ADaM) datasets will be prepared using Clinical Data Interchange Standards Consortium (CDISC) SDTM Implementation Guide (IG) Version 3.3, ADaM Version 2.1, and CDISC ADaM IG Version 1.2 including most current occurrence and time to event IGs.

4.3. Partial Dates

Imputation of partial adverse event and concomitant medication dates are specified in [Appendix 1](#), respectively.

All data recorded on the case report form will be included in data listings.

4.4. Data Conventions

The precision of original measurements will be maintained in summaries, when possible.

Quantitative safety laboratory tests containing less than (<) and greater than (>) symbols are test results that are below and above quantifiable limits, respectively. In order to retain these values for analysis purpose, the following will be imputed and stored within the analysis datasets:

- For values with <, the imputed value will be the numeric portion \times 0.9.
- For values with >, the imputed value will be the numeric portion \times 1.1.

Variables with a non-normal distribution that impacts the interpretation or validity of the planned analysis may have a data transformation applied (e.g., ln, \log_{10}).

4.5. Standard Calculations

Variables requiring calculation will be derived using the following formulas:

- Days – A duration expressed in days between one date (*date1*) and another later date (*date2*) will be calculated using the following formulas:
 - duration in days = $date2 - date1 + 1$, where $date1 \geq$ first administration date
 - duration in days = $date2 - date1$, where $date1 <$ first administration date
- Months – A duration expressed in months is calculated as the number of days divided by 30.4375
- Weeks – A duration expressed in months is calculated as the number of days divided by 7
- Years – A duration expressed in years between one date (*date1*) and another date (*date2*) is calculated using the following formulas:
 - duration in years = $(date2 - date1 + 1)/365.25$, where $date1 \geq$ first administration date
 - duration in years = $(date2 - date1)/365.25$, where $date1 <$ first administration date
- Body Mass Index (BMI) – BMI is calculated using height (cm) and weight (kg) using the following formula:
$$BMI \text{ (kg/m}^2\text{)} = \text{weight (kg)} / ([\text{height (cm)} / 100]^2)$$
- Change (CHG) – Change will be calculated as:
$$\text{Change} = \text{later value} - \text{earlier (i.e., baseline) value}$$
- Percent change (PCHG) – Percent change will be calculated as:
$$\text{Percent change} = ([\text{Change}] / \text{earlier [i.e., baseline] value}) \times 100$$

4.6. Treatments

Table 3 presents how the dose groups will be presented on TFLs as treatment groups, including the order.

Table 3: Treatment Group Labels and Ordering

Treatment Group Label	Order on TFLs	
Placebo	1	
Rodatristat ethyl 300 mg BID	2	
Rodatristat ethyl 600 mg BID	3	
Total Rodatristat ethyl	4	

Treatment Group Label	Order on TFLs	
Overall (where specified)	5	For summaries where specified in Sections 6 and 8.2

Screen failures will be presented on by-subject listings where data is available.

4.7. Visits

4.7.1. Windows

Each visit will be denoted by its visit “Week”. The first dose day is denoted as Day 1. In data listings, the relative study day of all dates from first dose will be presented.

Unless otherwise specified, scheduled assessments will be used for tabulated summaries. In the event of unscheduled visits, follow-up, or early treatment termination (ET) assessments, these will be reassigned to a scheduled visit for analysis purposes according to [Table 4](#) (RHC), [Table 5](#) (6MWT, WHO-FC, and NT-proBNP), [Table 6](#) (Clinical Laboratory Evaluations, Vital Signs, ECGs), and [Table 7](#) (Echocardiography and PAH-SYMPACT) for on treatment assessments. If multiple assessments occur within a single visit window, after reassignment of unscheduled visits and ET assessments, the assessment closest to the target day of the visit window will be used in the analysis. If there is a tie, the later assessment will be used in the analysis.

Table 4: Treatment Period Visit Windows: RHC

Target Scheduled Visit	Target Study Day ^a	Analysis Window Study Day ^a	
		Low	High
Baseline ^b	1	See Section 4.7.2	
Week 24	169	2	197 ^c

^a Study day will be calculated from first dose of study drug.

^b Baseline is defined in [Section 4.7.2](#).

^c Must be prior to first dose in the OLE.

Table 5: Treatment Period Visit Windows: 6MWT, WHO-FC, NT-proBNP

Target Scheduled Visit	Target Study Day ^a	Analysis Window Study Day ^a	
		Low	High
Baseline ^b	1	See Section 4.7.2	
Week 4	29	2	42
Week 12	85	43	126
Week 24	169	127	182 ^c

^a Study day will be calculated from first dose of study drug.

^b Baseline is defined in [Section 4.7.2](#).

^c Must be prior to first dose in the OLE.

Table 6: Treatment Period Visit Windows: Clinical Laboratory Evaluations, Vital Signs, and ECGs

Target Scheduled Visit	Target Study Day ^a	Analysis Window Study Day ^a	
		Low	High
Baseline ^b	1	See Section 4.7.2	
Week 4	29	2	42
Week 8	57	43	71
Week 12	85	72	105
Week 18	127	106	147
Week 24	169	148	182 ^c

^a Study day will be calculated from first dose of study drug.

^b Baseline is defined in [Section 4.7.2](#).

^c Must be prior to first dose in the OLE.

Table 7: Treatment Period Visit Windows: Echocardiography and PAH-SYMPACT

Target Scheduled Visit	Target Study Day ^a	Analysis Window Study Day ^a	
		Low	High
Baseline ^b	1	See Section 4.7.2	
Week 12	85	2	126
Week 24	169	127	182 ^c

^a Study day will be calculated from first dose of study drug.

^b Baseline is defined in [Section 4.7.2](#).

^c Must be prior to first dose in the OLE.

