5. ANALYSIS POPULATIONS

Table 8 defines the analysis populations to be used.

Table 8: Analysis Sets

Analysis Sets	Description
Screened	All subjects who sign the informed consent form (ICF).
Safety	All subjects who receive any amount of study drug. Treatment assignment will be based on the treatment actually received.
Intent-to-Treat (ITT)	All subjects randomized into any one of treatment groups. Treatment assignment will be based on the randomized treatment.
Modified Intent-to-Treat (mITT)	All ITT population subjects with an evaluable baseline and at least 1 post baseline PVR assessment. Treatment assignment will be based on the randomized treatment.
Per Protocol (PP)	All mITT subjects who have completed treatment with $\geq 80\%$ treatment compliance (actual, see definition in Section 8.1) without any major protocol deviations,. Treatment assignment will be based on the treatment actually received.
Treatment Completer	All mITT subjects who complete 24 weeks of treatment with no dose reductions or dose interruptions. Treatment assignment will be based on the randomized treatment. Sensitivity analyses may be conducted based on the treatment actually received. No missing data will be imputed for these analyses. Any substantial differences between conclusions based on the ITT, mITT and the completers' populations will be investigated.

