7.1.2.1. Missing at Random (MAR): Multiple Imputation

For the primary analysis of PVR, 6MWT, and NT-proBNP efficacy endpoints, subjects who miss an assessment for reasons other than death or other tolerability reasons, will be imputed using multiple imputation (MI) methodology based on the treatment group for time points at which no value is observed. An intercurrent event meeting will be held prior to database lock and unblinding with the medical monitor(s) and statistician(s) to review the missing efficacy assessments for each subject and determine if the missing data is MAR or missing not at random, (MNAR), i.e. informative missing.

MI will be performed under the assumption of MAR. Intermittent missing value(s) will also be replaced using MI. MI will impute 10 integer values using Markov Chain Monte Carlo (MCMC) methods assuming nonmonotone missing, a seed of 100201, 500 burn-in iterations, 100 iterations between imputations, and a non-informative prior. The imputation models based on treatment group will include randomization stratification factors, baseline WHO FC, baseline 6MWD, and baseline value of the endpoint and all previous values of the endpoint at each time point. Other baseline characteristics that may be explored will be documented in the CSR. It is anticipated that the imputation model will converge but should it not do so terms will be removed from the model to achieve convergence. The effects of any such model adjustment will be investigated.

Change from baseline to each post-baseline visit will be calculated based on observed and imputed data. Results from the analysis of each of the 10 imputed datasets will be combined using PROC MIANALYZE (Rubin's imputation rules, [Rubin 1987](#)).

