7.1.2.2. MNAR: Imputation for Deaths and Tolerability Reasons

For the primary analysis of PVR, 6MWT, and NT-proBNP efficacy endpoints, subjects who missed an assessment due to death, tolerability, or >10% change in parental prostainoid dose (including adding a new medication).will be imputed as the worst value in their planned treatment group at the specific visit.

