7.1.2.4. Other Assessments of Missing Data

To assess the impact of missing data and robustness of the results, the following sensitivity analyses will be performed for the primary and secondary endpoints:

- Observed case analyses
- Treatment Completers population analyses

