7.2. Primary Efficacy Analysis

The primary efficacy analysis will test the following hypothesis:

- H_0 : The mean change from baseline in PVR at Week 24 is equal between placebo and rodatristat ethyl.
- H_1 : The mean change from baseline in PVR at Week 24 is different between placebo and rodatristat ethyl.

In cases of missing data occurring at Week 24, missing data handling rules are specified in [Section 7.1.2](#).

Percent change from baseline in PVR at Week 24 will be analyzed using an analysis of covariance (ANCOVA) model with terms of treatment, randomization strata and baseline PVR. Estimates of least-square (LS) means, standard errors (StdErr), and 95% CIs will be presented by treatment group. In addition, the LS mean difference comparisons between each active dose and placebo, the StdErr of the difference, and 95% CI of the difference will be presented.

In order to control the Type 1 error rate, the comparisons between each active arm and the placebo arm will be tested using the Hochberg approach, where the two p-values (600 mg vs placebo and 300 mg vs placebo) will be ordered largest to smallest as $p(1) > p(2)$.

1. If $p(1) < 0.05$ then reject both null hypotheses.
2. If $p(1) > 0.05$, but $p(2) < 0.025$, then reject the null hypothesis associated with $p(2)$.

Assumptions for the ANCOVA will be checked, and if not satisfied, parametric analyses will be corroborated with appropriate nonparametric analyses, such as the Wilcoxon rank sum test stratified by randomization strata. The Hodges-Lehmann estimation of location shift and confidence interval will be produced. If the model residuals are not normally distributed, ANCOVA analysis based on ranked data will be performed.

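### Does the SAP leave open whether an early-termination catheterization or the worst-value rule supplies the Week 24 PVR?

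*SAP*

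**What the plan says.** **Windowing.** Under SAP 4.7.1, scheduled assessments are used by default. For the rest: "In the event of unscheduled visits, follow-up, or early treatment termination (ET) assessments, these will be reassigned to a scheduled visit for analysis purposes", by Tables 4 to 7, "for on treatment assessments". For RHC, Table 4 has a single post-baseline row, "Week 24 169 2 197": target Day 169, window Day 2 to Day 197, and before any open-label dose. If several RHCs fall in the window, the one nearest Day 169 is used.

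**When an early RHC exists.** Protocol 1.3 (footnote 14) and 8.2.1 ask for an RHC when a patient stops early, but only after at least 12 weeks of study drug and no later than 7 days after stopping. Protocol 8.2.1 also asks patients who stop drug to keep attending through Week 24, where an RHC is scheduled.

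**Missing data.** The link from the primary analysis in SAP 7.2 is conditional: "In cases of missing data occurring at Week 24". Section 7.1.2.1 confines multiple imputation to time points without an observed value. Section 7.1.2.2 gives the worst value in the planned arm to "subjects who missed an assessment due to death, tolerability, or >10% change in parental prostainoid dose (including adding a new medication". The pre-lock meeting in 7.1.2.1 is held "to review the missing efficacy assessments for each subject and determine if the missing data is MAR" or not. SAP Section 11 records that imputation and worst value replaced the protocol's last-observation rule.

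**Sensitivity analyses.** Section 7.1.2.4 lists "Observed case analyses" and an analysis of Treatment Completers, defined in Section 5 as "All mITT subjects who complete 24 weeks of treatment with no dose reductions or dose interruptions".

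**The concern.** The SAP announces that it has dropped last observation carried forward for PVR, yet Table 4 keeps the same number for anyone whose sole post-baseline RHC is early. Section 7.1.2.2 names tolerability as a reason for the worst value, and tolerability is a common reason for stopping. A patient who stops for that reason, has an RHC on leaving and never attends Week 24 might be said either to have a Week 24 value, through Table 4, or to have missed Week 24, under 7.1.2.2.

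Three further points add to the doubt:

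- The prostanoid trigger in 7.1.2.2 is not in itself a reason to skip an RHC. If the rule covers only absent RHCs, this trigger has almost nothing to act on for PVR.
- The pre-lock meeting reviews missing assessments, and a windowed RHC is not missing.
- The observed-case analysis uses the same windowed value, and the completer analysis removes other patients too. Neither isolates the early RHCs.

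At stake is the primary-endpoint value of perhaps a few patients in arms of 30, and the risk that the choice is made with results in view.

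**Working it through.** **1. Reproduce the design figure.** Inputs from SAP Section 3: 30 per arm, SD 24, difference 18, two-sided 0.05, power at least 80%.

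- Standard error = 24 × √(2/30) = 6.20. Noncentrality = 18 / 6.20 = 2.90 on 58 degrees of freedom.
- Power = 0.815 by the noncentral t (0.828 by the normal approximation). The stated figure is met.

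**2. Put the clauses in order for a patient with one early RHC and no Week 24 RHC.**

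| Step | Clause | Result |
|---|---|---|
| 1 | 4.7.1 and Table 4 | The RHC lies between Day 2 and Day 197, so it becomes the Week 24 value |
| 2 | 7.2 | The imputation rules are called only if Week 24 is missing. It is not |
| 3 | 7.1.2.1 | Applies where nothing is observed. Something is |
| 4 | 7.1.2.2 | Applies to a missed assessment. That phrase governs all three triggers |

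Every step gives the same answer: the measured PVR is used.

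**3. Patient with both an early RHC and a scheduled Week 24 RHC off drug.** The on-treatment phrase sits in the sentence on reassigning unscheduled, follow-up and early-termination assessments. A scheduled Week 24 RHC needs no reassignment. The nearest-to-target rule agrees: an RHC on Day 84 is 169 − 84 = 85 days from target, and one on Day 169 is 0 days away. The early RHC itself falls within 7 days of stopping. That is inside the SAP's one explicit on-treatment limit, last dose plus 30 days in 7.4.6, although that limit was written for time to clinical improvement.

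**4. Cost of the rule as written.** The number of affected patients, k, is not in the documents; take k = 1, 2, 3 of 30, all in one active arm. Assume that half the effect is present at the early RHC.

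Expected difference = 18 × (1 − k/30 × 0.5)

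| k | Difference | Loss | Power |
|---|---|---|---|
| 0 | 18.0 | 0 | 0.815 |
| 1 | 17.7 | 0.3 | 0.802 |
| 2 | 17.4 | 0.6 | 0.788 |
| 3 | 17.1 | 0.9 | 0.774 |

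If the effect is complete at Week 12, the factor 0.5 becomes 0 and the loss is zero.

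**5. What the other reading would do.** Suppose the k patients instead received the worst value among the rest of their arm. In a simulation of 100,000 trials (normal data, unadjusted t-test):

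| k, active arm only | Difference | Power | Conclusion differs from step 4 |
|---|---|---|---|
| 1 | 16.4 | 0.717 | 9% of trials |
| 2 | 14.8 | 0.609 | 18% |
| 3 | 13.2 | 0.501 | 27% |

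The gap between readings is about 1.3 points per patient; for k = 3, (17.09 − 13.20)/3 = 1.30. If all k are on placebo, conclusions differ in 5, 9 and 12% of trials; with one or three in each arm, in 5 or 12%.

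These figures show that precedence would matter if it were open. Step 2 shows that it is not.

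**6. Can a reader see the early RHCs?** Yes. Section 7 lists every efficacy endpoint by subject, and Sections 4.1 and 4.7.1 put relative study day on the listings. The Treatment Completer analysis omits all early terminators, and Section 5 commits to investigating substantial differences from ITT and mITT.

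**The case for a change.** The best case for acting is that it is cheap: one sentence on precedence, one on how long after the last dose an RHC still counts, and one extra run of the primary model treating RHCs before Day 127 as missing. Settled before unblinding, these would remove any later argument about a value that feeds the primary test. The prostanoid trigger is the strongest textual support, because on the plain reading it does little for PVR.

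Two parts of this stand. No sentence states precedence for 7.1.2.2. No planned analysis keeps these patients while handling their PVR differently, because the completer analysis also drops everyone with a dose reduction or interruption.

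The rest is weaker. A trigger that rarely fires does not thereby override measured data, and 7.1.2.2 also serves 6MWT and NT-proBNP. The 50% cap on prostanoid infusion counts users, not patients whose dose changes by more than 10%. The Day 127 cut is the midpoint of the Week 12 and Week 24 targets in Tables 5 and 7, (85 + 169)/2. RHC has no Week 12 visit, and Table 6 starts Week 24 at Day 148, so Day 127 is not a general SAP standard. As early RHCs begin at about Week 12, the extra run would alter only those from roughly Day 84 to Day 126, a group that the documents give no means of sizing.

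**Conclusion.** No change follows. The SAP omits a sentence that its other clauses make redundant: an RHC observed in the Table 4 window is the Week 24 PVR, and imputation applies only when there is none. An analyst following 4.7.1, 7.1.2 and 7.2 would do this, and using a measured value taken after at least 12 weeks of treatment is sound. That it equals the protocol's carried-forward number does not make it wrong.

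On that reading the cost is at most 0.9 points of 18, and about 4 points of power (0.815 to 0.774). This assumes three affected patients in one active arm and half the effect at the early RHC; the cost is zero if the effect is complete by Week 12. The larger figures, up to 27% of trials changing conclusion, need both the reading that the text does not support and a one-sided placement of patients. All counts are assumed. Protocol 8.2 expects withdrawal to be uncommon, and patients who stop drug are still asked to attend Week 24.

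A precedence sentence would only write down the rule that already applies. A further sensitivity analysis would be a matter of preference and would correct no wrong result.
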